The proposed design is a two-armed multicenter prospective cohort study with un-blinded standardized evaluation of pre-specified study outcomes in two defined separate and parallel cohorts of study participants. Sub-studies addressing specific research questions will be nested in the main cohorts. Pilot interventional clinical trials will also be performed on subsets of participants of the main cohorts. Up to two thousand participants will be enrolled into the NEPTUNE longitudinal cohorts over the enrollment period from the initial start date of December 11, 2009. The minimum follow-up period will be 36 months and subsequent annual in-person visits and/or chart abstraction for laboratories, vital and end-stage renal disease status may be conducted pending additional funding. The study will be comprised of two arms: Cohort A, a biopsy group composed of two main cohorts and Cohort B, a treatment-naïve, non-biopsy group of children less than 19 years of age. In the Cohort A (biopsy group), the two main cohorts will be specified by histopathologic criteria obtained from a baseline renal biopsy and pre-specified inclusion criteria. The first main cohort will be comprised of participants with histopathologic features consistent with Focal and Segmental Glomerulosclerosis (FSGS) or Minimal Change Disease (MCD) and the second histopathology cohort of Membranous Nephropathy (MN). Combined these Cohort A subsets are targeted to include a minimum of 300 participants to be enrolled under Protocol V4.1. These new enrollees will augment those enrolled under previous NEPTUNE protocol versions. Participants will be enrolled at academic clinical centers in the United States and Canada. The sampling frame is a consecutive series of all eligible and consenting patients undergoing diagnostic renal biopsy for any glomerular disease with the exception of renal disease due to systemic diseases such as lupus erythematosus (SLE), diabetes mellitus or multiple myeloma. A recruit-to-replace strategy will be utilized to ensure that a minimum sample size of 600 participants with FSGS, MCD and MN and 36 months of observation is preserved by the end of the recruitment period. After an initial pre-screening, participants will undergo a screening/eligibility visit, baseline visit, biopsy visit, and subsequently four month-interval follow-up visits during year one and thereafter, six month-interval follow-up visits after biopsy. Each participant will experience 9-10 study visits depending on date of enrollment and subsequent chart review and/or annual visits as funding and study timeline permits. Procedures to be performed during study visits include diagnostic baseline kidney biopsy, laboratory studies, blood and urine collection for biorepository, limited clinical examination, and administration of questionnaires. The primary study outcome of the two main biopsy cohorts are a change in urinary protein excretion and renal function. Several secondary outcomes will be evaluated including but not limited to composite of death, metabolic and hematologic complications, malignancies and infections. Descriptive and hypothesis-driven data analysis of the biopsy cohort studies will be performed at 30, 45 and 60 months of the study. For the FSGS/MCD cohort, a sample size of 250 participants is sufficient at two-sided alpha level of 0.05 to accurately predict the primary clinical outcome of Complete/Partial Remission vs. No Remission of urinary protein excretion (UPE) with a power of 75%-96%. For the MN cohort, a sample size of 200 participants is sufficient at two-sided alpha level of 0.05 to accurately predict the primary clinical outcome of Complete/Partial Remission vs. No Remission of urinary protein excretion (UPE) with a power of 70%-94%.

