3. STUDY METHODS

3.A. Study Design Overview

A prospective parallel cohort study generating three groups of participants, represented by two arms, will be performed in NEPTUNE. The two groups are: Cohort A which includes (1) the FSGS/MCD Cohort; and (2) the MN Cohort; as well as Cohort B – a non-biopsy, treatment-naïve, pediatric cohort less than 19 years of age, cNEPTUNE. The sample size for the combined FSGS/MCD and MN Cohorts is a minimum of 600 participants, with a minimum of 300 new patients recruited under Protocol V4.1 respectively. The sample size for the third group, cNEPTUNE, will be a minimum of 200 participants. Participants will be recruited into each subgroup concurrently. All participants who meet the inclusion criteria at the participating centers will be enrolled if the participants or their legally authorized representative(s) provide comprehensive written informed consent. A recruit-to-replace strategy will be employed throughout the enrollment phase. Cohort A study visits including screening/eligibility, baseline, biopsy, and follow-up visits are depicted in Appendix 8A. Study visits for Cohort B, cNEPTUNE, including screening/eligibility, baseline, follow-up visits, and SMS texting are shown in Appendix 8B.

3.A.1. Cohort A: FSGS/MCD and MN Cohorts

Pre-Screening: Potential participants will be identified by study team staff reviewing the medical records of patients being seen in clinic for diagnosis of kidney disease or patients presenting for a diagnostic renal biopsy. If necessary, a partial waiver of informed consent will be sought from the institutional review board to pre-screen these potential participants. Once pre-screened and identified, potentially eligible patients will be approached by a clinical caregiver to request permission for a study team member to initiate discussion of the NEPTUNE study.

Screening/Eligibility Visit [V_{SE}]: As an introduction to the NEPTUNE study, a study team member will meet with a potential participant, assess enthusiasm for the study, complete an eligibility questionnaire with the potential participant, and obtain informed consent if appropriate. If informed consent is obtained, an eligibility urine sample will be obtained for central laboratory processing at this first study contact, if not concurrent with the Biopsy Visit [V_{BX}]. The eligibility visit will last 30-45 minutes.

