In the first year, follow-up visits are expected to occur every four months after the baseline visit (see Appendices 8A and 8B, Visit Schedules), and subsequently every six months until the end of the study. Additionally, an unscheduled Relapse Visit can occur once annually per participant should a participant be scheduled to see their primary nephrologist giving an unscheduled visit window for each patient/year. In addition, the study protocol makes provision to include interval measures of renal function obtained for clinical purposes to be included in the study database.

3.C.2. Cohort A: Procedures During Screening/Eligibility [V_{SE}], Baseline [V1] and Biopsy [V_{BX}] Visits

General Principles: The Screening/Eligibility, Baseline, and Biopsy Visits period is expected to last at most 45 days around the time of renal biopsy. Before entering Baseline, participants will be screened to ensure that they meet the inclusion criteria and that none of the exclusion criteria are present. A de-identified screening log will be maintained in the study database.

Participants in the NEPTUNE cohorts will be followed for an initial period of up to 36 months or longer pending additional resources and depending on the date of enrollment. The following section describes the procedures to be implemented during the screening, baseline and follow-up phases of each cohort study.

3.C.2.a. Pre-screening

We will use a Forward Operating Study Subject (Participant) Awareness (FOSSA) System. The FOSSA System details that study personnel are trained to initiate screening at several points in the healthcare system where the opportunity exists to identify potential study participants. Study personnel screen medical records, appointment schedules and laboratory databases as consistent with local IRB protocols to identify patients who appear to meet inclusion/exclusion criteria.

3.C.2.a.(a) Screening/Eligibility [V_{SE}]

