Proteinuria (U:C) After Observation Period	Standard Definition	Definitions for the Cohorts
$U:C \leq 0.3g$	Complete Remission (CR)	Complete/Partial Remission
Reduction in U:C of $>50\%$ plus final $P:C \leq 3.5g$ but $>0.3g$	Partial Remission (PR)	
Reduction in U:C of $>50\%$ with final $P:C > 3.5g$	Limited Response (LR)	No Response
Reduction in U:C of $<50\%$. (include increase in U:C $<50\%$)	Non-Response (NR)	
Proteinuria increases by $>50\%$	Progressive Proteinuria (PP)	
New development of nephrotic range proteinuria, i.e., >3.5 P:C after reaching a complete or partial remission	Relapse	Relapse

3.E.1.b. Renal Function

The main renal function measures in the cohort studies include serum creatinine, serum Cystatin C, a 24-hour urinary clearance of creatinine, and estimated GFR using the MDRD equation for adults and modified Schwartz formula for continent children under 18 years. Serum Cystatin C assay will be deferred until funds for ancillary studies become available. The schedule of these measures is summarized in Table 4.

Table 4. Schedule of Renal Function Measurements in the NEPTUNE main cohorts

Measure	Collection Schedule
Serum creatinine	Every visit
24-hour urinary creatinine excretion	Every visit
Estimated GFR	Every visit
Serum Cystatin C	Every visit*

* Funds pending

3.E.1.b.(a) Creatinine-based Measures

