Two special populations bear a disproportionate burden with respect to FSGS as reflected in higher prevalence of disease: African Americans (AA) and the pediatric age group. Ideally, a sampling frame in which these two populations are overrepresented in the study cohort will enhance the ability of the proposing teams to test race-specific and pediatric age group-specific research hypotheses. We did not specify oversampling of the AA population because of the success in recruitment of AAs into the initial NEPTUNE cohorts and the large sample size necessary and the limited resources available to expand this to a distribution beyond that representing the racial distribution of individuals with the diseases of interest. A modest size pediatric cohort has been added to NEPTUNE as the cNEPTUNE cohort B which will only include children with incident disease. The study team envisions that future ancillary studies with supplementary recruitment of additional AA and pediatric participants would be pursued if the current proposal is successful in meeting its recruitment target. Notwithstanding this deferment, we would implement several steps to ensure that a significant fraction of the NEPTUNE participants in the current study are of AA race and pediatric age group, respectively. The steps to ensure this objective are: (1) inclusion of several pediatric nephrology programs in the participating clinical centers; (2) inclusion of clinical centers located in cities with two of the three largest AA populations in the US (Detroit and New York). The study team monitors the proportion of AA and pediatric participants enrolled as part of the recruitment monitoring plan and will be prepared to institute additional measures if either of these two important populations are underrepresented in the recruited cohort by study month 10 (one-third of the way through the 30-month recruitment period).

4.B. Retention Plan

In order to protect the power for statistical analyses of main research hypotheses, it would be necessary to maintain a retention rate of >85% by the end of the study. This means that the study cannot afford more than an annual average loss to follow-up rate exceeding 5%. Two periods are most vulnerable to patient dropout. Initially, patients

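### The biopsy-cohort analyses at study months 30, 45 and 60 do not fit the protocol's own recruitment and follow-up, and the remission endpoint has no fixed assessment time

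*Protocol*

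**What the plan says.** **Calendar.** Section 1.B states that descriptive and hypothesis-testing analyses of the biopsy cohorts "will be performed at 30, 45 and 60 months of the study". Enrolment runs "from the initial start date of December 11, 2009". The section adds: "The minimum follow-up period will be 36 months". Section 3.C.2 words this differently: participants "will be followed for an initial period of up to 36 months or longer". Section 4.A.3 places study month 10 "one-third of the way through the 30-month recruitment period", and section 4.B also gives a 30-month recruitment phase.

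**Sample.** Section 3.A sets at least 600 for the combined FSGS/MCD and MN cohorts, "with a minimum of 300 new patients recruited under Protocol V4.1". Section 1.B wants the 600 to have 36 months of observation. The power statements use 250 (FSGS/MCD) and 200 (MN). The Foreword says the major modifications followed a meeting on September 29, 2014.

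**Endpoint.** The first column of Table 3 is headed "Proteinuria (U:C) After Observation Period", and no length is given. Section 3.F.4 reduces the outcome to two classes, remission (complete or partial) against no remission or relapse. It models them by univariate and then ridge logistic regression. Section 3.F.5.e adds Cox and recurrent-event analyses.

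**The concern.** Two things do not fit together. First, the last scheduled analysis comes before the stated recruitment and follow-up can be complete, and well before participants enrolled under the current version could be followed for 36 months. As dated, no scheduled analysis can describe the cohort that the protocol sets out to assemble.

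Second, the primary classification has no assessment time. Remission status is reversible: section 2.A.6 cites about 30% relapse after complete remission in MN, and section 3.F.5.e expects participants to move between states. The month of assessment therefore helps decide who falls in which class. A logistic model has no censoring. If it is run at the early calendar dates without a landmark, participants are compared after very different lengths of observation, and a predictor can pick up length of follow-up along with prognosis.

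**Working it through.** **1. Recruitment plus follow-up.** The inputs are 30 months (4.A.3, 4.B) and 36 months (1.B). 30 + 36 = 66, against a last analysis at 60. Reaching 60 would take 24 + 36 or 30 + 30, and the protocol states neither pair.

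**2. Calendar dates from December 11, 2009.**
- Month 30: June 11, 2012
- Month 45: September 11, 2013
- Month 60: December 11, 2014
- Month 66: June 11, 2015

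**3. V4.1 enrollees.** The protocol gives no start date for V4.1 enrolment. Take September 29, 2014 as the earliest conceivable date. It is study month 57.6.
- Longest V4.1 follow-up at month 60: 60 − 57.6 = 2.4 months.
- Earliest month at which a V4.1 participant reaches 36 months: 57.6 + 36 = 93.6.
- Share of the minimum sample affected: 300/600 = 50%.

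**4. Share with full follow-up.** Assume uniform accrual over 30 months (not stated in the protocol). The share with 36 months at analysis month M is min(1, max(0, (M − 36)/30)).

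| Analysis month | Share with 36 months | Of 250 | Of 200 | Time since entry (months) |
|---|---|---|---|---|
| 30 | 0 | 0 | 0 | 0 to 30 |
| 45 | 9/30 = 30% | 75 | 60 | 15 to 45 |
| 60 | 24/30 = 80% | 200 | 160 | 30 to 60 |
| 66 | 30/30 = 100% | 250 | 200 | 36 to 66 |

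At month 60 everyone recruited within 30 months has at least 30 months of follow-up. The 250 and 200 can therefore all be present by head count.

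**5. Illustration of possible distortion.** Assume a constant remission hazard, no relapse, and that anyone not in remission at the data cut goes into the no-remission class. With true 36-month remission c, the hazard is λ = −ln(1 − c)/36. Observed remission at month M is the average of 1 − exp(−λ·min(36, M − t)) over entry times t from 0 to 30.

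| c at 36 months | Month 30 | Month 45 | Month 60 |
|---|---|---|---|
| 40% | 18.6% | 33.1% | 39.5% |
| 50% | 24.0% | 41.9% | 49.4% |
| 60% | 30.1% | 51.0% | 59.4% |
| 70% | 36.9% | 60.5% | 69.4% |

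In this model the gap is large at month 30, about 7 to 10 points at month 45, and at most 0.6 points at month 60.

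**The case against.** **The observation period is obviously 36 months.** Section 1.B asks for 36 months of observation and visits run to month 36, so this is the natural reading. But the protocol does not say it, 3.C.2 writes up to 36 months or longer, and the analyses at months 30 and 45 could not use it for most participants.

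**Short follow-up belongs to the SAP, and censoring is already planned.** Sections 3.F.1 and 3.F.5.e and Hypothesis 9 do use hazard rates or Cox regression, and detailed handling rules may well sit in an SAP that was not available here. That stands. It leaves the undefined term in the primary outcome table and the conflicting calendar. The main model is not in doubt: 3.F.4 names the binary prediction model as the primary objective of the data analysis.

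**The two timeline arguments rest on different accrual histories.** This is true: 66 months assumes one 30-month recruitment, and the V4.1 point assumes enrolment continuing in late 2014 or later. They are separate checks, and the schedule fails each one. Restarting the study clock in September 2014 would move month 60 to September 2019, but the protocol states no restart and 66 would still exceed 60.

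A reader might go further in four ways that the document does not support.
- *Short follow-up is scored as no remission.* No such rule is written. It is only a likely result of a binary class without a landmark.
- *V4.1 enrolment starts after month 60.* This is inferred from dates. The start is not given, and the meeting precedes month 60.
- *No analysis can contain the powered sample.* This is untrue by head count for the 250 and 200.
- *False-positive predictors will be common because case mix shifts.* Section 3.F.2 makes the recruitment correction conditional and adds weighting. The protocol gives no size of drift, and 3.F.4 illustrates thresholds of 10⁻⁴ and 10⁻⁸, far below 0.05.

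**Conclusion.** The point holds in two parts. The calendar conflict is plain arithmetic on stated figures: month 60 falls 6 months before 30 + 36. With the December 2009 origin, at least 300 of the minimum 600 could have no more than about 2.4 months of follow-up at the last scheduled analysis. That upper limit assumes V4.1 enrolment could not begin before the September 2014 meeting.

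The missing assessment time is also a fact of the text. Its effect depends on assumptions. Under uniform 30-month accrual, 0% and 30% of participants have 36 months at the first two analyses, against 80% at the third. Any resulting bias depends on the remission pattern, relapse and drift in case mix, none of which the protocol quantifies. In a simple model without relapse, bias could be substantial at months 30 and 45 and is negligible at month 60. The text needs correcting. The document does not show that a month-60 analysis of the 250 and 200 would be seriously biased.

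**What to change.** - **Section 1.B:** replace the three study-month dates with a follow-up rule. The main analysis is done when the last participant counted in the 600, V4.1 enrollees included, has completed the 36-month visit or been censored before it.
- **Table 3:** replace the undefined observation period with one fixed time from baseline, for example the 36-month visit.
- **Any earlier analysis:** restrict the binary endpoint to participants whose landmark has passed, or use the Cox analysis already planned in 3.F.5.e.
- **Sections 1.B and 3.C.2:** reconcile the minimum of 36 months with the wording that allows up to 36.

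The cost is time. The main analysis moves to as much as 36 months after the last counted enrolment. No extra patients or visits are needed.

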Other measures, including screen failure for consented individuals determined to have exclusion criteria present post-enrollment, have been taken to compensate for over-enrolling in the OG group. The OG group will not be further followed, but samples and data obtained will remain available for comparative analyses.

3.F.3. Special Considerations for the Analysis of Molecular Biomarkers

[figure not shown]
The analysis of molecular biomarkers aims to identify promising genetic signatures used in the building of a prediction model for clinical outcomes. To screen the large number of potential predictors without losing analytical power, we would proceed in a hypothesis generating manner. Regression analysis of the clinical endpoint on biomarkers allows us to obtain P-values in the testing of their association, and a threshold value of false discovery rate would be set to determine a pool of potentially important biomarkers. These selected biomarkers will then be analyzed and grouped according to the relevance of their biological functions available in various databases. For example, biomarkers in a common transcriptional network may form a molecular signature panel. Such various panels can be further tested for the association with the clinical endpoint via the method of ridge regression. Ridge regression enables us to bypass the analytic difficulty due to highly correlated biomarkers in the model and hence obtain robust results.

3.F.4. Prediction Model Combining Molecular Biomarkers and Auxiliary Variables

The primary objective of the data analysis is to build a predictive model that uses both molecular biomarkers and auxiliary predictors to classify patients into one of two clinical states of the primary endpoint, Complete Remission/Partial Remission (CR/PR) and No Remission/Relapse (NR/R). The second endpoint is the presence or absence of the loss of renal function. In addition to 20,000 molecular markers, there are 74 auxiliary predictors collected from both cohort studies, including 38 histopathology variables, 15 laboratory variables, 15 clinical and demographic information variables, and 6 treatment variables.

Given the large number of predictors, we take a three-stage data analysis strategy consisting of variable screening, model building, and model validation. Figure 1 shows a schematic flow of steps for the model building.

Figure 1: Schematic illustration of analytic steps taken to model building.

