The first stage of analysis is a variable screening analysis, in which we perform univariate analysis. The aim of this study is to evaluate basic distributional characteristics of each predictor and pairwise correlation between the response and each predictor, as well as that between each pair of predictors. In this analysis, we also examine if transformations on some predictors are needed and if high-order predictors such as interactions and polynomial predictors are potentially useful predictors.

At the second stage of analysis, we build a predictive model for the clinical endpoint. First, we perform univariate logistic regression of the clinical endpoint on each of the predictors to detect promising predictors. To deal with the multiplicity in the test, we control a common significance level α_m on molecular markers and α_c on auxiliary predictors. At different levels of α_m and α_c , we obtain several sets of molecular and auxiliary predictors. For example, we may control α_m at 10^{-8} and α_c at 10^{-4} according to the Bonferroni's conservative type I error control. Using a set of the selected predictors, we invoke ridge logistic regression to build a predictive model, which essentially provides a linear classifier to determine the membership of a patient with a clinical class.

At the final stage of model building, we use the ROC curve method to select the final model from a small pool of candidate predictive models. To do this, we split the sample into the training set and the test

set at $(2/3n):(1/3n)$ (96-98) randomly with multiple rounds, say 100. For the sample size 200, the split is 135:65, and for the sample size of 250, the split is 170:80. At each round, we use the training set to build a predictive model and the test set to evaluate its performance of prediction by the AUC, acronym for the area under the receiver operating characteristic (ROC) curve. We use the averaged AUC to determine the final predictor model with the best averaged prediction power.

3.F.5. Sample Size and Power Considerations

3.F.5.a. Overview

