The primary aim of this study is to build up the prediction model, so our sample size and power calculation should be based on this goal. Following Dobbin and Simon (96), we adopt the expected probability of correct classification (PCC) as the measure of predictive power, which is approximately equal to the AUC, acronym for the area under the receiver operating characteristic (ROC) curve. This study focuses on two rare diseases: FSGS/MCD and MN, so we use PCC to evaluate the sample size of these two diseases, respectively.

3.F.5.b. Sample Size and Power Related to the FSGS/MCD Cohort Study

PCC is the probability of correct classification obtained on an infinite sample size and should be the gold standard of the best power. FSGS and MCD are rare diseases; it is unrealistic to find very large sample sizes to approximate the result under an infinite sample size. However, we will be able to find the PCC under realistic sample sizes, and we use PCC* to denote it. PCC* is the expected probability of correct classification with the optimal linear classifier constructed from the true molecular markers and auxiliary predictors. The results given in Table 6 are based on a simplified analysis with conservative assumptions. We screen 20,000 genes (probes) and 75 auxiliary predictors, in which there are r_m true gene expression markers and r_c true auxiliary predictors for the clinical endpoint. Ratio δ_m/σ_m is the average effect size of a single molecular marker, and the relative effect size of the auxiliary predictor to the molecular marker is 0.5. Also, ρ is the correlation between molecular markers and auxiliary predictors, and $\rho=0$ is assumed in Table 7 (3.N-2 below).

Table 7. Probability of Correct Classification

$r_m = 5, r_c = 10$				
δ_m/σ_m	PCC*	PCC(n=100)	PCC(n=150)	PCC(n=200)
0.2	0.788	0.638	0.667	0.687
0.4	0.941	0.876	0.892	0.896
$r_m = 50, r_c = 10$				
δ_m/σ_m	PCC*	PCC(n=100)	PCC(n=150)	PCC(n=200)
0.2	0.941	0.638	0.695	0.753
0.4	0.999	0.987	0.995	0.996
$r_m = 100, r_c = 10$				
δ_m/σ_m	PCC*	PCC(n=100)	PCC(n=150)	PCC(n=200)
0.2	0.982	0.672	0.766	0.837
0.4	0.99999	0.9994	0.99990	0.99994

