For example, if we have 50 molecular markers and 10 auxiliary variables, from the sample size of 200, we will be able to reach a 99.6% PCC* with the average effect size of a single molecular marker to be 0.4, and the relative effect size of the auxiliary predictor to the molecular marker to be 0.5. This 99.6% PCC* almost reaches the optimum PCC of 99.9%, yet it is very realistic because the sample size of 200 falls in our recruitment targets.

It is noted that the inclusion of patients without the specified diseases of interest will not affect the power of classifier designed for this study as long as the required sample sizes given

in Table 7 are met. Such additional information from the third cohort might be useful in the development of a different classifier in an auxiliary study where the clinical status of these patients is of interest.

3.F.5.c. Sample Size and Power Related to the MN Cohort Study

Under the same assumption given in the power calculation for the FSGS/MCD cohort study, we can also calculate the power of the MN cohort study in the same fashion. And the result provided in Table 7 above (3.N-1) can also be applied to the MN cohort study.

For example, if we have 100 molecular markers and 10 auxiliary variables, from under the sample size of 150, the PCC* is 76.6% with δ_m/σ_m being 0.2 and the relative effect size of the auxiliary being 0.5. If we increase the sample size from 150 to 200, we can find an increase of PCC* from 76.6% to 83.7%.

3.F.5.d. Sample Size and Power Related to the cNEPTUNE Study

The analytic plan for this cohort is to identify groups of participants by clinical relapse and remission patterns as well as functional, molecular and genetic profiles, with a goal to relate those groups to clinically meaningful outcomes, including patient reported outcomes. As these subgroups are yet to be defined by the data obtained by the cohort, we present a range of exposures and minimum detectable odds ratios below. In the pediatric population, and as seen in the current NEPTUNE cohort, rates of clinically significant decline in kidney function, defined as a 40% drop in eGFR or ESRD, ranged from 0.00 to 0.16 per person-year, and as such, the study is not primarily powered to this event.

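### The synopsis states power at two-sided alpha 0.05, but section 3.F.5 tabulates only classification accuracy, and two PCC* cells of Table 7 conflict with the stated relative effect of 0.5

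*Protocol*

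**What the plan says.** Section 1.B gives two sample-size statements. The first reads "For the FSGS/MCD cohort, a sample size of 250 participants is sufficient at two-sided alpha level of 0.05" and continues to "Remission vs. No Remission of urinary protein excretion (UPE) with a power of 75%-96" per cent. The second reads "For the MN cohort, a sample size of 200 participants is sufficient at two-sided alpha level of 0.05" and gives 70%-94% for the same remission contrast.

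Section 3.F.5.a takes a different basis: "we adopt the expected probability of correct classification (PCC) as the measure of predictive power, which is approximately equal to the AUC". Section 3.F.5.b sets out the assumptions for Table 7: 20,000 probes are screened, r_m = 5, 50 or 100 of them are true markers, r_c = 10 auxiliary predictors are true, the marker effect delta_m/sigma_m is 0.2 or 0.4, molecular and auxiliary predictors have zero correlation, and "the relative effect size of the auxiliary predictor to the molecular marker is 0.5". Table 7 has columns for PCC* and for n = 100, 150 and 200. Section 3.F.5.c adds that "the result provided in Table 7 above (3.N-1) can also be applied to the MN cohort study".

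Section 3.F.4 describes how models are built and compared by AUC on repeated splits: "For the sample size 200, the split is 135:65, and for the sample size of 250, the split is 170:80".

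**The concern.** Power at a stated alpha is the chance that a test rejects. PCC is the chance that a classifier puts a patient in the right class. The synopsis reports the first, while the sample-size section works only with the second. A reader therefore cannot trace 75%-96% or 70%-94% to any calculation in the protocol.

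Other sections lean on these figures. Section 3.F.2 raised the recruitment target to 600 so as to keep statistical power with 250 and 200 participants in the two cohorts. Section 4.B sets a retention rate above 85% to protect that power.

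Table 7 is the only quantitative support for 250 and 200. If part of it does not follow from its stated inputs, either the table or the sentence describing those inputs is wrong, and the reader cannot tell which.

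**Working it through.** **1. Looking for the synopsis ranges in section 3.F.5.**

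- Table 7 has no n=250 column.
- At n=200 its six cells are 0.687, 0.896, 0.753, 0.996, 0.837 and 0.99994. The range is 68.7% to 99.99%, not 70% to 94%.
- The worked examples are 99.6% for FSGS/MCD (at n=200, not 250), and 76.6% (n=150) and 83.7% (n=200) for MN.
- No finite-n cell equals 0.94 or 0.96. The value 0.941 appears only under PCC*.
- Alpha 0.05 with 80% power appears in 3.F.5 only for cNEPTUNE (3.F.5.d).

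**2. Trying to reproduce the ranges as power.** The protocol names no test, so I assumed a two-sided 0.05 two-sample comparison of one marker with equal classes, taking the listed effects as the full between-class difference in SD units. Power at n=250 is 0.352 (effect 0.2) and 0.885 (effect 0.4). At n=200 it is 0.293 and 0.807. If the listed effects are half-differences, power at 0.2 becomes 0.885 (n=250) or 0.807 (n=200), and at 0.4 it is about 1. Neither range appears.

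**3. Trying to reproduce them as AUC.** For an equal-variance normal score with equal classes, AUC = Phi(sqrt(2) × Phi^-1(PCC)).

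- r_m=5, n=200: 0.687 → 0.7547 and 0.896 → 0.9625. This is 75% to 96%, the FSGS/MCD range, but at n=200 rather than 250.
- r_m=5, n=100: 0.638 → 0.691 and 0.876 → 0.949. This is near 70% to 94%, but at n=100 rather than the 200 named for MN.

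Because one table serves both cohorts, MN at n=200 would have to carry the first range, not the second.

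**4. Checking PCC\* in Table 7.** I read PCC\* as the limiting value, as the column is used. For an optimal linear classifier on independent normal predictors, with k the relative auxiliary effect:

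S = (delta_m/sigma_m)^2 × (r_m + k^2 × r_c), PCC\* = Phi(sqrt(S)).

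This form is an assumption, because the protocol prints none.

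| r_m | effect | printed | S, k=0.5 | PCC\*, k=0.5 | S, k=1 | PCC\*, k=1 |
|---|---|---|---|---|---|---|
| 5 | 0.2 | 0.788 | 0.3 | 0.708 | 0.6 | 0.781 |
| 5 | 0.4 | 0.941 | 1.2 | 0.863 | 2.4 | 0.939 |
| 50 | 0.2 | 0.941 | 2.1 | 0.926 | 2.4 | 0.939 |
| 50 | 0.4 | 0.999 | 8.4 | 0.998 | 9.6 | 0.999 |
| 100 | 0.2 | 0.982 | 4.1 | 0.979 | 4.4 | 0.982 |
| 100 | 0.4 | 0.99999 | 16.4 | 0.99997 | 17.6 | 0.99999 |

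At k=0.5 the two r_m=5 cells miss by 8.0 and 7.8 points, and the other four are within 1.5 points. At k=1 all six are within 0.8 points. The closest alternative at k=0.5, the AUC form Phi(sqrt(2S)), gives 0.980 against the printed 0.941 for r_m=50 at effect 0.2.

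**5. A check that needs no effect-size convention.** Whatever the scaling, PCC\* increases with S. Table 7 prints 0.941 both for r_m=5 at 0.4 and for r_m=50 at 0.2. Equal values need

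0.16 × (5 + 10k^2) = 0.04 × (50 + 10k^2), so 0.8 + 1.6k^2 = 2.0 + 0.4k^2, so k = 1.

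At k=0.5 the two sides are 1.2 and 2.1.

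**6. Finite-n columns.** An approximation by marker selection gives 0.640, 0.668 and 0.689 at k=1 for the r_m=5, effect 0.2 row (printed 0.638, 0.667, 0.687), against 0.541, 0.549 and 0.561 at k=0.5. At k=1 it misses the r_m=5, effect 0.4 row by 2.4 to 3.8 points. Since the protocol's method for these columns is not shown, this is supporting evidence only.

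**The case against.** The strongest reply is that power in section 1.B is shorthand for predictive power, the phrase that 3.F.5.a attaches to PCC. Step 3 supports this: the r_m=5 values at n=200 convert to exactly 75% and 96%. That stands as a plausible origin. A reader might infer that the figures were invented or never calculated, and the documents do not support that. The reply does not rescue the statement as printed, because the sizes do not match and an alpha level has no meaning for a classification accuracy.

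A second reply is that Table 7 is mostly sound. This is also fair: four of six PCC* cells agree with the stated 0.5 within 1.5 points, and both worked examples use r_m=50 or 100, where PCC* barely moves.

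A reader might further infer that the accuracies are too favourable in general. That is not established:

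- If a relative effect of 1 was intended, the PCC* column stands and only the sentence giving 0.5 is wrong.
- Equating PCC with AUC understates AUC (0.687 against 0.755), which is the opposite direction.
- Section 3.F.3 expects ridge regression to "bypass the analytic difficulty due to highly correlated biomarkers in the model", but it gives neither the sign nor the size of the correlations. Their effect on PCC* can go either way, depending on the signs of the marker effects.

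Finally, the splits of 135:65 and 170:80 serve to compare candidate models, and both training sizes lie within the tabulated range of 100 to 200. Reporting accuracy there would be useful, but its absence is not an error.

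**Conclusion.** Two inconsistencies stand.

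First, the power and alpha statements in 1.B have no counterpart in 3.F.5. This can be seen from the protocol alone: the metric differs, no alpha is used for these cohorts, n=250 is not tabulated, and the n=200 range is 0.687 to 0.99994. Mislabelled AUC is a possible source, on the assumption of an equal-variance normal score.

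Second, the r_m=5 PCC* cells conflict with the stated relative effect of 0.5 by about 8 points under the standard formula, which is assumed. That some conflict exists does not depend on the effect-size convention, because the repeated 0.941 requires equal effects. The documents do not show whether the sentence or the table is wrong.

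These are errors of reporting and traceability. They should be corrected, but they do not show that 250 and 200 are too few, and no analysis rule or participant protection depends on them.

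**What to change.** - In 1.B, replace the power and alpha wording with the expected PCC, or the AUC labelled as such, at n=250 and n=200. Give the derivation and the assumed r_m and effect size. Preferably report the training sizes of 170 and 135 as well.
- In 3.F.5.b, state whether the relative auxiliary effect was 0.5 or 1. Then correct either the sentence or Table 7. If the table changes, recompute its finite-n columns too and print the formula or cite the exact method.
- In 3.F.5.a, remove the claim that PCC and AUC are nearly equal, or give the conversion.
- While editing, use PCC* consistently. The worked examples attach it to finite-n values, whereas the table uses it for the limit.

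The cost is one recomputed table and a few sentences. No more participants are needed.
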